Protocol Synopsis

Modulation of GABA-A Receptors in Parkinson Disease-Flumazenil Arm

NCT03462641

12/14/2020

Axial motor impairments represent a significant cause of disability in Parkinson disease (PD), which is mainly explained by a lack of efficacy of dopaminergic treatments of these symptoms. Treatment approaches to reduce balance problems and falls have been recently identified as the number 1 research priority in PD. Postural instability and gait difficulties (PIGD) motor features are mediated by widespread neural networks that extend well beyond the nigrostriatal system. There is increasing interest in dysfunction of non-dopaminergic neurotransmitters to better understand the complexity of the multisystem nature of mobility impairments in PD. Flumazenil is a short-acting intravenously administered modulator of the γ -aminobutyric acid-A (GABA-A) receptor benzodiazepine binding site, which has shown to rapidly improve motor impairments in PD. Based upon current basal ganglion models in PD, flumazenil could normalize neuronal signaling of hyperGABA-ergic activity in PD.

We have preliminary data that reduced cerebral GABAA receptor availability (likely reflecting increased synaptic or extracellular GABA-ergic activity) as determined by [^{11}C]flumazenil PET imaging has most robust association with axial compared to other cardinal motor impairments in PD. Although flumazenil therapy has been shown to improve motor symptoms in PD, its practical limitation is that it can only be effectively and reliably given intravenously. The overarching goal of this project is to perform biomechanistic GABAA receptor target engagement studies to investigate the effects of GABAA receptor modulation to motor impairments in PD, including PIGD features using i.v. flumazenil vs placebo in a cross-over study design to be correlated to pretreatment C11-flumazenil PET thalamic binding. Our main hypothesis is that negative allosteric modulation of cerebral GABAA receptor activity improves dopamine-resistant PIGD features.

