Statistical Analysis Plan

Modulation of GABA-A Receptors in Parkinson Disease-Flumazenil Arm

NCT03462641

05/31/2022

In this proposal, the investigators present data suggesting that flumazenil (FMZ) administration leads to a decrease in postural instability and gait disorder (PIGD) symptoms of Parkinson's Disease (PD). Further association is made between treatment effectiveness and GABA-A receptor FMZ PET thalamic binding at baseline.

Study participants were pseudo-randomly assigned into A and B sequences, and came in for two visits, with sequence A participants receiving FMZ infusion on the first visit and sequence B participants receiving saline infusion (placebo) on the first visit. The other treatment was given on the subsequent day for participants in both sequences. Detailed motor examination including modified UPDRS was conducted on both days prior to infusion and at 60-90 minutes postinjection. UPDRS PIGD motor subscale score was computed as our primary outcome measure. FMZ PET imaging was done to collect data for the test of interaction between treatment and GABA-A receptor availability.

A paired samples t-test was conducted for each participant's pre and post infusion PIGD score for the flumazenil pharmacological injection treatment only to test whether FMZ pharmacological injection appears to have any effect on PIGD score in a univariate comparison. A repeated measures ANOVA model was used to test the significance of interaction between treatment (FMZ pharmacological injection vs. placebo) and time of administration (pre-infusion vs. post-infusion), with additional three-way interaction term between treatment, time of administration, and sequence (A vs B) included to account for potential confounding effect of sequence. Lastly, a mixed linear model comparison was conducted between the random intercept model and FMZ PET by treatment interaction model, to test the hypothesis that the effect of flumazenil pharmacological i.v. treatment on change in PIGD scores depends on baseline GABA-A FMZ PET receptor availability in the thalamus. Bilaterally averaged thalamic FMZ PET distribution volume ratio (DVR) by treatment (FMZ pharmacological therapy injection vs placebo) was used for the interaction term, and difference between PIGD scores (post – pre) infusion were used as a response variable for that model.

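### Must the test of thalamic DVR by treatment also carry a baseline-severity by treatment term?

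*SAP*

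**What the plan says.** The analysis paragraph of the SAP says that "a mixed linear model comparison was conducted between the random intercept model and FMZ PET by treatment interaction model". The response is the post-minus-pre difference in PIGD, and the predictor of interest is bilaterally averaged thalamic DVR by treatment. The hypothesis is that the effect of flumazenil "treatment on change in PIGD scores depends on baseline GABA-A FMZ PET receptor availability in the thalamus". The opening paragraph puts the aim in similar terms: "Further association is made between treatment effectiveness and GABA-A receptor FMZ PET thalamic binding at baseline".

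No baseline-severity covariate or severity-by-treatment term is described for this model. The data for one exist, since the design paragraph records that "Detailed motor examination including modified UPDRS was conducted on both days prior to infusion".

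The Protocol Synopsis gives the wider purpose, to "perform biomechanistic GABAA receptor target engagement studies", and the background: "We have preliminary data that reduced cerebral GABAA receptor availability" ("likely reflecting increased synaptic or extracellular GABA-ergic activity") "has most robust association with axial compared to other cardinal motor impairments in PD". It gives no coefficient for that link, and does not name the thalamus or PIGD in it.

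**The concern.** The Synopsis gives reason to expect patients with lower receptor availability to have worse axial signs. If flumazenil also removes a larger number of PIGD points in patients who start worse, low-DVR patients will improve more simply because they have more to lose. The DVR-by-treatment slope is then real but says nothing about the receptor beyond severity.

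The direction of the slope does not help. If low availability marks excess GABA-ergic activity that flumazenil corrects, a receptor effect would also give more benefit at lower DVR (my inference from the Synopsis). For a project with a mechanistic aim, the risk is that a positive slope is read as receptor-specific when the model cannot show that.

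**Working it through.** **Inputs.** The documents give no sample size, SD, correlation or effect size, so there is no planned figure to reproduce and every number here is an assumption. True PIGD severity has mean 5 and SD 2. Examination error has SD 1. Flumazenil reduces PIGD by a fraction *f* of 20% or 40%, with no placebo effect. DVR is in SD units with correlation ρ to severity. Trials have 20 or 30 participants.

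**1. Which term matters.** Take D, each person's flumazenil change minus placebo change. A person-level main effect cancels from D, so only severity by treatment can alter the DVR slope. In a simulated 30-person dataset the slope was 0.577 as planned, 0.577 with mean pre-infusion PIGD as a main effect, and 0.240 with its treatment interaction.

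**2. Slope produced by severity alone.** Planned model: *f* × 2 × |ρ|.
- ρ = -0.5: 0.2 × 2 × 0.5 = 0.20 and 0.4 × 2 × 0.5 = 0.40 points per SD of DVR.
- ρ = -0.7: 0.28 and 0.56.

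**3. What is left after adjustment.** The mean of two pre-infusion scores has error variance 1/2 = 0.5. Given DVR, severity has variance 4(1 - ρ²). The fraction of slope remaining is 0.5 / [4(1 - ρ²) + 0.5].
- ρ = -0.5: 0.5/3.5 = 0.143, and 0.40 × 0.143 = 0.057.
- ρ = -0.7: 0.5/2.54 = 0.197, and 0.56 × 0.197 = 0.110.

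**4. How often the slope is significant.** t-test of the slope of D on DVR, two-sided 5%, 20,000 replicates per cell, simulation standard error at most 0.4 percentage points. Cells show planned / with severity by treatment.

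| n | ρ | *f* = 20% | *f* = 40% |
|---|---|---|---|
| 20 | -0.3 | 5.5% / 5.2% | 7.4% / 5.0% |
| 20 | -0.5 | 7.0% / 5.0% | 12.2% / 5.2% |
| 20 | -0.7 | 8.7% / 5.0% | 19.8% / 5.4% |
| 30 | -0.3 | 6.0% / 4.9% | 9.0% / 5.1% |
| 30 | -0.5 | 8.3% / 5.1% | 16.5% / 5.4% |
| 30 | -0.7 | 11.0% / 5.1% | 28.9% / 5.5% |

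Both conditions are needed. Detection is 4.9-5.1% with zero correlation and 4.7-5.1% with a constant drug effect. The planned-column excesses are not type I errors, because the marginal slope is truly non-zero. With error SD 0.5-1.5 and PIGD SD 1.5-3 (ρ = -0.5, *f* = 40%), planned detection runs over 6.9-40% at n = 20 and 8.2-57% at n = 30.

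**5. What adjustment costs.** With residual variance held equal, the slope variance grows by 1/(1 - r²) × (n - 3)/(n - 4), where r² = ρ² × 4/4.5. At ρ = -0.5 and n = 20: r² = 0.222, and 1/0.778 × 17/16 = 1.37. At ρ = -0.3 and -0.7 the ratio is 1.15 and 1.88.
- Mean 95% CI half-width for ρ = -0.5 to -0.7 rises from 1.00-1.05 to 1.16-1.37 (n = 20) and from 0.78-0.82 to 0.90-1.06 (n = 30). Both exceed the 0.20-0.56 at issue.
- Power for a genuine DVR effect of 1 point per SD falls from 53% to 48%, 41% and 32% at n = 20, and from 72% to 68%, 60% and 47% at n = 30, for ρ = -0.3, -0.5 and -0.7.
- At n = 20 and ρ = -0.5 to -0.7, a significant planned slope shrinks by more than 30% in 22-54% of severity-only trials and in 8-17% of trials with a genuine DVR effect.

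**6. The reference model.** The SAP does not list its fixed effects. I set a treatment effect of 0.8 residual SD, no modification by DVR, residual SD 1 and random-intercept SD 0.5. A likelihood-ratio comparison with an intercept-only reference then rejects in 35.9%, 55.1% and 72.7% of runs at n = 10, 20 and 30. With both main effects in the reference it rejects in 9.8%, 6.5% and 5.9%. The t-test of the interaction coefficient rejects in 5.3%, 4.6% and 4.8%.

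**The case for a change.** The best case for a change is that the protocol's aim is mechanistic, its own background makes a DVR-severity correlation plausible, and the scores are already collected. One further fit brings severity-only detection back to about 5%. Using the mean of the two pre-infusion scores also avoids the usual coupling of baseline with change: with equal, independent errors, (e1 + e2)/2 is uncorrelated with the pre-score part of the contrast, e2 - e1.

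The algebra stands, and so does the limit on interpretation: the planned slope alone cannot show that DVR matters beyond severity. The step from there to a changed plan does not.
- Neither document claims independence from severity, and neither says that benefit scales with it.
- The caveat on a positive slope would be the same whatever the companion model showed. A non-significant adjusted slope could reflect lost precision, and shrinkage separates the readings poorly.
- Severity may lie on the path from receptor change to response. Adjusting for it could then discard the effect being sought, and reasonable statisticians would differ on doing so.

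A separate objection is that the comparison may not test effect modification at all if its reference is intercept-only. That is a fair reservation about the SAP's wording, but it does not bear on severity. The hypothesis names the interaction, so an analyst would naturally read the interaction coefficient or keep both main effects in the reference.

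**Conclusion.** No change to the plan follows. Omitting severity by treatment is a fair trade-off, and adding it would bring little gain. The coefficient addresses the hypothesis as stated, an association between response and thalamic DVR, provided it is tested on its own or against a reference holding the treatment and DVR main effects. The SAP leaves that condition unstated; I take it as a gap that analysts would fill sensibly, and do not endorse an intercept-only comparison.

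Severity alone could yield a significant slope in 7.0-28.9% of trials across n = 20-30 and correlations of -0.5 to -0.7, and in 5.5-9.0% at -0.3. These figures rest entirely on assumed inputs and require both a DVR-severity correlation and a benefit that scales with severity. If either is absent there is no excess. A positive result is best described as an association that may reflect baseline severity. A severity-adjusted fit would be optional and exploratory, and post hoc if the analysis has been run, as the SAP's past tense suggests.
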